This will be a single-center, double-blinded, parallel-group, randomized, placebo-controlled trial. Older adults with sarcopenic obesity (n= 105) will be allocated to one of three groups: protein supplementation (PTN, n=35), placebo supplementation (PLA, n=35), or control (CON, n=35). The PTN and PLA groups will receive dietary supplements in addition to an exercise training and calorie restriction intervention, while the CON group will receive no intervention. Body composition, bone health, cardiorespiratory fitness, pulmonary function, functional capacity, muscle cross-sectional area, upper and lower-limb maximal dynamic strength, endothelial function, biochemical parameters, health-related quality of life, cognitive function, sleep quality, symptoms of anxiety and depression, and nutritional status will be assessed before and after a 16-week intervention period. A linear mixed model with repeated measures analysis will be conducted to assess within- and between-group effects of the intervention, using baseline values of the outcome as covariates. Whenever significant group-by-time interactions will be found, post-hoc tests on the adjusted predictions with Sidak's adjustment will be performed for multiple comparisons. Significance will be set at $p<0.05$. Data will be reported as the mean and standard deviation, along with the estimated mean difference (EMD) between groups and its 95% confidence interval (95% CI) when a main effect or interaction is observed.

BACKGROUND AND SIGNIFICANCE

The prevalence of obesity among older adults is growing worldwide (1-3). Excessive adipose tissue is linked to insulin resistance, high blood pressure, endothelial dysfunction, and dyslipidemia, obesity offers a heightened risk for developing cardiovascular and metabolic diseases, particularly among older individuals (4-6). Concurrently, aging is associated with declines in skeletal muscle mass and function (i.e., sarcopenia) (7), which can be further exacerbated by obesity (8-10). The interplay of these conditions poses an emergent public health issue termed sarcopenic obesity (11-13), a condition associated with greater risk of morbimortality and worse health-related quality of life (14, 15).

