Men and women aged 65 years or older, with central obesity (waist circumference >102 cm for men and >88 cm for women), body mass index (BMI) of ≥ 30 kg/m², sarcopenia (according to the criteria set by the Foundation for the National Institutes of Health (FNIH) (68)), not engaged in an exercise training program, and with stable weight within the past 6 months will be considered eligible to participate. Reference cut-off values for sarcopenia will include a handgrip strength-to-BMI ratio of less than 1.0 kg/BMI and an appendicular fat-free mass-to-BMI ratio of less than 0.789 kg/BMI for men, and a handgrip strength-to-BMI ratio of less than 0.56 kg/BMI and an appendicular fat-free mass-to-BMI ratio of less than 0.512 kg/BMI for women (68).

Exclusion criteria

Exclusion criteria will include a history of recent malignancies (within the past 5 years); cognitive deficits or dementia that prevent the participant from reading and signing the informed consent form; and medical conditions in which physical testing or engaging in exercise training would be contraindicated (e.g., locomotor disabilities or cardiopulmonary diseases, including unstable angina, heart failure, myocardial infarction, or chronic obstructive pulmonary disease).

Follow-up procedure:

In case of drop-out, the participant will be asked to complete a full set of examinations at the time of drop out.

STUDY DESIGN

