The present study will be a single-center, double-blinded, parallel-group, randomized, placebo-controlled trial. Figure 1 illustrates the study design. Initially, participants will be pre-screened through phone calls or personal interviews. Those who meet the preliminary criteria will then be further assessed for their medical condition and eligibility criteria. Eligible participants will be matched based on sex and then randomly allocated in a 1:1:1 ratio into one of the following experimental groups: (a) protein supplementation (PTN), (b) placebo supplementation (PLA), or (c) control (CON). Both the PTN and PLA groups will receive dietary supplementation, will be caloric-restricted, and will engage in an exercise training program. Participants in the CON group will receive no intervention other than general guidance on healthy eating and physical activity. All outcomes of interest will be assessed immediately before participants' randomization at baseline (PRE) and after 16 weeks of intervention (POST). Anthropometric and dietary parameters will be reassessed at weeks 4, 8, and 12. Participants will also meet with a registered dietitian from the research team every two weeks in order to ensure compliance with the dietary intervention.

RANDOMIZATION

Eligible participants will be sex-matched and then randomly allocated using a computer-generated block design in a 1:1:1 ratio into one of the following experimental groups through a specific software (<https://randomizer.org>): (a) protein supplementation (PTN), (b) placebo supplementation (PLA), or (c) control (CON). The allocation sequence will be concealed from the research staff.

EXAMINATIONS

The primary outcome will be the change from baseline in fat-free mass (total, appendicular, appendicular relative to BMI and leg). Secondary outcomes will include other measures of body composition (i.e. fat and bone density), bone microarchitecture, bone metabolism, and specific muscle functions. Other outcomes, including cardiopulmonary capacity (cardiorespiratory fitness and pulmonary function), glycemic control, insulin sensitivity, endothelial function, inflammation, cognitive function and

related cellular and molecular mechanisms (telomere length, oxidative stress, and lipid profile) will also be assessed.

Anthropometry

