Sample size was determined a priori using the G-Power software (Version 3.1.9.2, University of Kiel, Germany). The analysis was conducted by inputting α error (0.05), power ($1 - \beta$ error = 0.95), and effect size (Hedges' g = 0.61), considering previous data indicating a lower loss of fat-free mass in individuals undergoing caloric restriction who had an increase in protein intake compared to their counterparts who maintained their usual protein intake (31). Calculations were based on an ANOVA with repeated measures (within-between interactions) and the total sample size was determined to be 81 individuals. To account for midtrial withdrawals, the sample will be increased by ~30% (i.e. 105 participants).

DATA ANALYSIS

Data will be presented as mean \pm standard deviation (SD), estimated mean difference between groups (EMD) at POST (only in the presence of group x time interaction), 95% confidence interval (95%CI), unless otherwise indicated. Baseline characteristics will be compared between groups using either Fisher exact test or generalized linear model with Sidak post hoc adjustment whenever necessary. Data will be analyzed using an intention-to-treat (ITT) approach to preserve the integrity of randomization. Before inferential analysis, outliers will be identified, and the data will be tested for homogeneity of variance and sphericity. Dependent variables will be analyzed by a linear mixed model analysis for repeated measures (assuming time [PRE and POST] and group [PTN, and PLA] with baseline values as covariate. The restricted maximum likelihood method, compound symmetry covariance structure, and Kenward-Roger degrees of freedom approximation will be applied for all models. In order to maintain the overall significance level at 0.05, the primary endpoints will be assessed using Hochberg's procedure (124). For all secondary outcomes the significance level will be set at $p \leq 0.05$. Whenever significant group-by-time interactions are identified, post-hoc tests on the adjusted predictions with Sidak's adjustment will be performed for multiple comparisons.

All analyses will be performed in the statistical environment R (version 3.5.3; R Core Team 2020).

STATISTICAL ANALYSIS PLAN

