All analyses will be performed in the statistical environment R (version 3.5.3; R Core Team 2020). We will perform all the comparisons using two-sided significance tests. Intention-to-treat analyses will be performed by analyzing data from all participants originally randomized to preserve the integrity of randomization. The longitudinal analysis of all outcomes will be performed using a linear mixed model for repeated measures, assuming 'group' (PTN, and PLA) and 'time' (pre-intervention and post-intervention) as fixed factors, and 'subjects' as a random factor, with an interaction between 'group' and 'time' added to the model; baseline values of the outcome will be used as covariates. For all models, maximum restricted likelihood and Kenward-Roger degrees of freedom will be used for model fit and estimation. We will adjust for testing of the four primary outcomes, total fat-free mass, appendicular fat-free mass, appendicular fat-free mass relative to body mass index, and leg fat-free mass, using Hochberg's procedure in order to maintain the overall significance level at 0.05. Since the other hypothesis tests (for the secondary outcomes) will be more exploratory in nature, the Hochberg's correction will not be used, and two-sided p-values less than 0.05 will be considered to indicate statistical significance. For both primary and secondary outcomes, whenever significant group-by-time interactions are identified, post-hoc tests on the adjusted predictions with Sidak's adjustment will be performed for multiple comparisons.

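### Allocation is matched on sex but no analysis model contains sex, which could leave the group standard error about 1–3% too large

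*Combined protocol and SAP*

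**What the plan says.** The allocation restriction appears twice in the combined protocol and SAP. RANDOMIZATION: "Eligible participants will be sex-matched and then randomly allocated using a computer-generated block design in a 1:1:1 ratio". STUDY DESIGN: "Eligible participants will be matched based on sex and then randomly allocated in a 1:1:1 ratio". Neither section says whether the blocks are formed within sex.

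The analysis model is described in three places:

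- SUMMARY OF STUDY specifies a repeated-measures mixed model "using baseline values of the outcome as covariates".
- DATA ANALYSIS gives the terms as "assuming time [PRE and POST] and group [PTN, and PLA] with baseline values as covariate", and adds "compound symmetry covariance structure, and Kenward-Roger degrees of freedom approximation will be applied for all models".
- STATISTICAL ANALYSIS PLAN has group and time as fixed factors and subject "as a random factor, with an interaction between" group and time, and states that "baseline values of the outcome will be used as covariates".

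Sex is in none of these models, and no sex-adjusted or sex-stratified analysis is planned.

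Both sexes are enrolled. Inclusion criteria sets sex-specific limits on a quantity that is also one of the four primary outcomes: "appendicular fat-free mass-to-BMI ratio of less than 0.789 kg/BMI for men", against 0.512 for women.

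**The concern.** When allocation balances a factor that predicts the outcome, the treatment estimate already has the benefit of that balance. A model that omits the factor leaves its variance in the residual, so the reported standard error exceeds the true one, intervals are too wide and power is lost.

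The primary outcome here is change in fat-free mass, so only a sex difference in change matters. A difference in level alone does no harm to a change contrast. Nor does the omission bias the estimate, unless withdrawals differ by sex and arm together.

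The baseline covariate might be expected to stand in for sex. In a model with PRE and POST both as responses, a baseline main effect does not enter the within-subject change, so it helps less than it would in an ANCOVA on POST.

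**Working it through.** The plan has no figure on this point to reproduce.

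**Inputs from the documents.** 35 per arm; contrast PTN versus PLA, the two groups named in the model; g = 0.61 and two-sided alpha 0.05.

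**Assumptions.** 60% women (14 men and 21 women per arm); sex exactly balanced; within-sex SD of change = 1; sex difference in change d; baseline separating the sexes by 2.6 within-sex SD; change unrelated to baseline within sex.

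**Closed form.** With p the share of men, the SE excess in an analysis of within-subject change is sqrt(1 + p(1-p)d²) - 1. Here p(1-p) = 0.4 × 0.6 = 0.24.

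- d = 0.3: sqrt(1 + 0.24 × 0.09) = sqrt(1.0216), an excess of 1.1%.
- d = 0.5: sqrt(1 + 0.24 × 0.25) = sqrt(1.06), an excess of 3.0%.

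At 50% men the excess is 1.1 and 3.1%; at 20% men it is 0.7 and 2.0%.

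**Simulation.** The plan leaves the fit open, so three were run, with 20,000 trials per setting: (a) compound symmetry allowing negative covariance; (b) random subject effect with variance held non-negative, plus the baseline covariate; (c) ANCOVA on POST with baseline. Each was fitted without and with sex (sex-by-time in a and b).

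| | d = 0.3 | 0.5 | 0.8 | 1.0 |
|---|---|---|---|---|
| SE excess (a), % | 1.1 | 3.1 | 7.6 | 11.6 |
| SE excess (b), % | 0.8 | 2.3 | 5.5 | 8.4 |
| SE excess (c), % | -0.1 | 0.7 | 2.4 | 4.1 |
| Power gained (a), points | 0.8 | 2.1 | 5.2 | 8.2 |
| Power gained (b), points | 0.4 | 1.3 | 3.4 | 5.2 |
| Power gained (c), points | -0.3 | 0.5 | 1.9 | 3.0 |

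The SEs at d = 0.5, without versus with sex, are:

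- (a) 0.2455 v 0.2382, ratio 1.031
- (b) 0.2431 v 0.2377, ratio 1.023
- (c) 0.2416 v 0.2399, ratio 1.007

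The benchmark is sqrt(2/35) = 0.239. The estimate's actual spread stays near that value, so it is the unadjusted model SE that is too large. Type I error without sex at d = 0.3 / 0.5 is 4.7 / 4.1% for (a), 4.9 / 4.4% for (b) and 5.0 / 4.6% for (c).

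**Sensitivity.**

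- If baseline does not separate the sexes, all three fits give about 1.1 / 3.1 / 7.6 / 11.8%.
- At d = 0.5, with baseline separation of 0 to 2.6 SD and a within-sex baseline-change correlation of -0.29 to 0.29, (b) runs from 1.7 to 5.1% and (c) from -0.3 to 7.3%.
- With 50 to 80% women, (b) at d = 0.5 is 1.6 to 2.3%.

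**Which term is needed.** In the mixed model a sex main effect alone recovers none of the loss under (a). Under (b) at d = 0.5 it recovers 0.55 of 2.27%, about a quarter.

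**Is a sex difference in change plausible?** The eligibility limits have the ratio 0.789 / 0.512 = 1.54. Under equal percentage change, if women's mean change were 0.5 to 1 SD (assumed), men would differ by 0.54 times that, or 0.27 to 0.54 SD. These are limits, not means.

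**Withdrawal.** The calculated 81 is 27 per arm, so 8 of 35 may leave. The bias is about d times the gap in male share among those remaining.

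- 2 men and 6 women lost in one arm, 4 and 4 in the other: 12/27 - 10/27 = 0.07; bias at d = 0.5 is 0.04 SD, 6% of 0.61.
- 1 and 7 against 5 and 3: 13/27 - 9/27 = 0.15; bias 0.07 SD, 12% of 0.61.
- Withdrawal at random: under (b) the bias is at most 0.003 SD.

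**The case against.** The strongest objection is that no document figure shows a sex difference in change. The only anchor is a ratio of eligibility limits for one of four primary outcomes, and those describe level. BACKGROUND AND SIGNIFICANCE presents exercise and protein as countermeasures to lean-tissue loss, so mean change could be near zero.

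Equal percentage change would also make the sex gap differ by arm. Applying the 1.54 ratio arm by arm (values are women's mean change in SD) gives these excesses under (a) and (c):

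- PTN 0, PLA -0.61: 0.3% and -0.35%
- PTN +0.305, PLA -0.305: 0.0% and -0.5%
- PTN -0.39, PLA -1: 1.7% and 0.2%

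This stands. The ratio is weak support unless both arms move appreciably in the same direction, and the 1–3% is conditional on an assumed difference.

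Three further points also stand in part. Under a POST ANCOVA, adding sex can cost slightly more than it returns. The withdrawal splits are illustrative, and Follow-up procedure asks those who drop out for a full examination, which would reduce that risk. Matching is not defined as blocks within sex, so balance is assumed.

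It is also said that the reasoning covers only fat-free mass. The SE figures are in SD units and carry over to any outcome with the same standardised sex difference, but the plausibility argument does not.

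None of this disputes that sex is matched at allocation and absent from every model.

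**Conclusion.** The point holds as a minor efficiency matter that the sponsor could improve. The allocation balances sex and the analysis does not use it. For an assumed sex difference in change of 0.3 to 0.5 SD, the mixed-model SE is about 1 to 3% too large and the test slightly conservative, with no bias from the omission itself. The size rests on 35 per arm, sex balanced between arms and roughly 30 to 50% men; at 20% men the closed form gives 0.7 to 2.0%. It vanishes if the sexes change alike and nearly vanishes under a POST ANCOVA when baseline separates the sexes well. No result of the trial is invalidated.

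**What to change.** Pre-specify sex as a covariate for all outcomes, in the form that suits the fit: sex plus sex-by-time in the PRE/POST mixed model, or sex as a fixed effect if an ANCOVA on POST is used. The interaction with time is the term that matters in the mixed model. State in RANDOMIZATION how the matching is done, in particular whether blocks are formed within sex.

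STUDY TIME LINE ends in August 2023 while the reference list includes 2024 papers, so this text was finished after that date. If outcome data had been seen by arm, keep the stated model and report the sex-adjusted one as a labelled sensitivity analysis.

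The cost is one sentence in the SAP and one degree of freedom for the time contrast, plus one between subjects for the main effect. Sex is already recorded for eligibility and matching. If sex does not predict change given baseline, the mixed-model SE is unchanged and the POST ANCOVA SE rises by about 0.5%.

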glycemic control and insulin sensitivity, endothelial function, inflammation, and related cellular and molecular mechanisms (telomere length, oxidative stress, and lipid profile). We hypothesized that this integrated approach could provide substantial benefits for body composition, and various health-related outcomes crucial to managing sarcopenic obesity in this population.

STUDY HYPOTHESIS

We hypothesized that protein supplementation can provide additional benefits on body composition and bone health more than only caloric restriction and exercise training in this population. Additionally, we hypothesized that these improvements would enhance muscle function. Furthermore, we also expected that protein supplementation would enhance the effects of caloric restriction and exercise training on glycemic control, insulin sensitivity, endothelial function, inflammatory markers, lipid profile, telomere length and oxidative stress markers.

AIM

This study aimed at investigating the impact of protein supplementation in addition to exercise training and caloric restriction on fat-free mass (as primary outcome) in older adults with sarcopenic obesity. Secondary outcomes include skeletal muscle fiber area, muscle strength and functionality, fat mass (total, visceral and subcutaneous), bone health parameters (bone mineral density, microarchitecture and bone metabolism markers). In addition, this study will aim the effects of protein supplementation in other outcomes including cardiopulmonary capacity (cardiorespiratory fitness and pulmonary function), glycemic control and insulin sensitivity, endothelial function, inflammation, and related cellular and molecular mechanisms (telomere length, oxidative stress, and lipid profile).

RESEARCH DESIGN AND METHODS

This 16-week study will be a single-center, double-blinded, parallel-group, randomized, placebo-controlled trial.

STUDY POPULATION

Older adults will be recruited from the Division of Geriatrics at the School of Medicine of the University of São Paulo, as well as through advertisements on social media and in community-based centers for older adults. All participants will provide written informed consent before enrollment in the study.

Inclusion criteria

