Quadriceps mCSA will be evaluated through computed tomography (CT) scans (Discovery CT 750HD, GE Healthcare, Chicago, IL). PRE and POST images will be acquired by the same blinded specialized radiology technician, under medical supervision, and processed using GE Healthcare workstation. To avoid bias, both will be blinded to the participants' group assignment. Initially, an image will be captured to determine the thigh length, which will be defined as the perpendicular distance from the greater trochanter to the inferior border of the lateral epicondyle of the femur. Quadriceps mCSA images will be acquired at 50% of the segment and processed using GE Healthcare workstation. Image acquisition parameters will be as follows: slice thickness = 10 mm; table increment = 10 mm, 0.70 rev/s, 120 kV, 68 mAs per slice, and field of view = 500. Density values used will range from 30–100 HU. Quadriceps mCSA will be determined using computerized planimetry through the 'freehand region of interest (ROI)' tool of the image analysis software Isite PACS 4.1 (Philips Healthcare Informatics, 4100 East Third Ave., Suite 101 Foster City, CA, USA).

Rectus femoris and vastus lateralis muscular cross-sectional area

Rectus femoris and vastus lateralis mCSA will be assessed by a B-mode ultrasound with a 7.5-MHz linear-array probe (LOGIQ e PRO – GE Healthcare, Chicago, IL, US) as previously described (71). Similarly to CT scans, images will be obtained at 50% of the segment. This anatomical point will be transversally marked every 2 cm with semipermanent ink and used as a reference for the probe displacement. Sequential images will be acquired, aligning the superior edge of the probe with each mark on the skin following a middle-to-lateral direction. To avoid pressure on the muscle tissue, which could result in image distortion, a generous amount of conductive gel will be used. After the data collection, the muscle images will be reconstructed in PowerPoint (Microsoft, Redmond, WA, USA). mCSA will then be measured using computerized planimetry (i.e., by contouring following the muscle fascia using an 800-dpi mouse) (Madena 3.2.5; Eye-

Physics, Los Alamitos, CA, USA). The planimetry software (ImageJ, NIH, USA) will be calibrated with fixed distance scales displayed in the US images. A single investigator, blinded to the participants' group assignment, will perform the analyses.

Visceral and subcutaneous fat areas

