Visceral (VAT) and subcutaneous adipose tissue (SAT) areas will be measured by CT scans (Discovery CT 750HD, GE Healthcare, Chicago, IL). Similarly, the same blinded specialized radiology technician will acquire the images at PRE and POST under medical supervision and process them using the GE Healthcare workstation. First, an image will be initially obtained to determine the umbilical scar, which will allow the delineation of total and visceral adipose tissue areas (72).

VAT will be assessed using the following procedures: (i) the technician will manually draw a line below the skin to obtain the total adipose tissue, which will be defined as the sum of adipose tissue hounsfield units (HU) inside this line, and (ii) VAT will be segmented by drawing a line, which begins at the abdominal linea alba, bisects the rectus abdominis, the internal oblique, the iliocostalis, and laterally around the peritoneum surrounding the vertebral body to join at the midline anterior to the vertebral body. All HU inside this line that meet the criteria for adipose tissue X-ray density will be counted as visceral adipose tissue (73).

Abdominal SAT area will be determined by the difference between VAT and total abdominal fat, by using computerized planimetry through the 'freehand ROI' tool of the image analysis software Isite PACS 4.1 (Philips Healthcare Informatics, 4100 East Third Ave., Suite 101 Foster City, CA, USA). Image acquisition parameters will be as follows: slice thickness = 10 mm; table increment = 10 mm, 0.70 rev/s, 120 kV, 68 mAs per slice and field of view = 500. Density values used will range from -30 to -190 HU.

Muscle biopsies

Prior to tissue extraction, the area will be cleansed with an antiseptic solution. Subsequently, the selected site will be anesthetized with a subcutaneous injection of 3 mL of 2% lidocaine. Following local anesthesia, a small incision (~5 cm) will be made down to the muscle fascia using a surgical scalpel. A Bergström biopsy needle will then be inserted into the lateral portion of the vastus lateralis at a depth of approximately 4 cm, adjusted based on the thickness of subcutaneous fat (74). Suction will be applied to the

outer end of the needle using a 120 mL syringe, allowing a small muscle tissue sample to be excised by the needle's internal blade (75). After the needle is withdrawn, pressure will be applied to the incision site to prevent bleeding, and the incision will be closed and covered with sterile bandages (76).

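### The abdominal CT level for visceral and subcutaneous fat is set by the umbilicus, with no stated rule that POST reproduces the PRE level

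*Combined protocol and SAP*

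**What the plan says.** Under Examinations, the section on visceral and subcutaneous fat areas describes one level-setting step: "First, an image will be initially obtained to determine the umbilical scar, which will allow the delineation of total and visceral adipose tissue areas". The only mention of the spine there is as an in-plane border of the visceral contour, which runs "laterally around the peritoneum surrounding the vertebral body to join at the midline anterior to the vertebral body". That border shapes the region on an image already chosen; it does not choose the level.

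The consistency measures are about operator and scanner. Both visits are handled alike in that "the same blinded specialized radiology technician will acquire the images at PRE and POST under medical supervision", and the settings are fixed ("slice thickness = 10 mm; table increment = 10 mm, 0.70 rev/s, 120 kV, 68 mAs per slice and field of view = 500"). The section gives no repeatability figure for VAT or SAT and does not state the number of abdominal slices.

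The quadriceps CT is placed differently. Its image is taken at half the thigh length, defined as "the perpendicular distance from the greater trochanter to the inferior border of the lateral epicondyle of the femur".

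The Aim lists "fat mass (total, visceral and subcutaneous" among the secondary outcomes. The inclusion criteria require participants "with central obesity (waist circumference >102 cm for men and >88 cm for women", together with a BMI of at least 30. The section on caloric restriction sets a deficit of 300-500 kcal/day for PTN and PLA; CON receives general guidance only.

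**The concern.** The umbilicus lies in the abdominal wall, the tissue that the intervention is meant to change. If its height relative to the spine differs between PRE and POST, the two areas are measured at different anatomical levels. Because VAT and SAT areas vary along the abdomen, part of the recorded change would then be a change of level rather than of fat. With 10 mm slices, a shift of one 10 mm increment is enough for the two slices not to overlap.

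Scatter in the shift between participants would widen the standard error of the PTN-versus-PLA difference. A shift with a consistent direction would bias the within-group change, which the Summary of Study says will be assessed. It would also bias any comparison of a weight-losing arm with CON. The sample size was set for fat-free mass, so the documents show no power margin for VAT or SAT.

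**Working it through.** **1. Side by side: how the plan fixes the site of its level-dependent measures.**

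| Measure | What fixes the level | Repeatability given |
|---|---|---|
| Thigh CT | 50% of a segment between two bony points | no |
| Waist circumference | midpoint of lowest rib and iliac crest | no |
| HR-pQCT of the radius | 9.5 mm from a reference line | CV 0.93-1.41% (density), 1.49-7.59% (structure) |
| Abdominal CT | umbilical scar | no |

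Of these four, only the abdominal CT rests on a soft-tissue landmark, and its section has no rule linking POST to PRE.

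**2. Size.** The plan states no figure here that could be reproduced. It gives no level shift, no VAT gradient along the abdomen and no SD of VAT change. All three inputs below are assumptions:

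- g, VAT gradient: 3-8% per cm
- s, SD of the PRE-to-POST level shift: 0.5-2 cm
- D, SD of true VAT change: 15% or 25%

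If level error is independent of true change, the error SD is g × s, and the standard error of the difference in change is multiplied by √(1 + (g·s/D)²).

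| g × s | Error SD | SE increase, D = 15% | SE increase, D = 25% |
|---|---|---|---|
| 3% × 0.5 cm | 1.5% | √1.010 = 1.005, 0.5% | √1.004 = 1.002, 0.2% |
| 3% × 1 cm | 3% | √1.040 = 1.020, 2% | √1.014 = 1.007, 0.7% |
| 5% × 1.5 cm | 7.5% | √1.250 = 1.118, 12% | √1.090 = 1.044, 4% |
| 8% × 2 cm | 16% | √2.138 = 1.462, 46% | √1.410 = 1.187, 19% |

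The result depends strongly on all three inputs, so only the range is informative. The same formula applies to SAT with its own gradient and SD.

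**3. What added variance would cost in power (illustration only).** Take a two-sided 5% comparison of two means with 35 per arm. Borrow the standardised difference of 0.61 from the fat-free-mass calculation. If level error adds 0%, 10%, 25%, 50% or 100% to the variance of change, power is 72%, 68%, 63%, 55% or 44%. This is not a check of the plan's own power of 0.95, which concerns another outcome and another test.

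**4. Direction.** A mean shift common to PTN and PLA cancels in their difference; only its scatter between participants remains, as noise. In a single arm the mean shift does not cancel. With the same assumed gradient, a systematic 1 cm shift would add or hide 3-8% of VAT (1 cm × 3-8% per cm) in that arm's change, and the sign is unknown.

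**The case against.** The strongest reply is that the documents nowhere say that the umbilicus moves with fat loss, or by how much. That is anatomical reasoning, and it stands as a limit. A reader might infer that PRE and POST areas do come from different vertebral levels. The text supports only that nothing stated prevents it. The section does not say whether the technician consults the PRE image at POST. It also cites an earlier trial for the method, which may hold a matching rule that cannot be checked here. That a single slice is measured is itself inferred from the reporting of areas.

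A reader might also infer that the PTN-versus-PLA result is biased. Both arms have the same planned deficit, so a shift driven by fat loss should be similar on average and largely cancel. Bias there would need the arms to differ in abdominal fat loss. Even the noise requires scatter between participants, which is assumed here.

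Bias against CON is tempting too, but the Data Analysis section and the SAP list only PTN and PLA as groups, so no CON contrast for VAT or SAT is specified. It would arise only in a descriptive comparison.

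Finally, the size rests wholly on assumptions. Nothing converts the planned energy deficit into a shift in centimetres, and one case falls from 12% to 4% when the assumed SD of change goes from 15% to 25%.

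These points reduce the concern but do not remove it. Using the same technician and the same settings does not fix the anatomical level, and the team already uses bony references elsewhere.

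**Conclusion.** The point holds in a limited form. The plan leaves an avoidable source of measurement error in the PRE-to-POST change in VAT and SAT: it relies on a soft-tissue landmark and states no rule for matching levels. The likely consequence is noise in the modelled PTN-versus-PLA comparison, with possible bias in within-group change and in any descriptive comparison with CON. Its size is unknown. The range of under 1% to about 46% in the standard error rests entirely on the assumed gradient, shift and SD, and no single value in it should be singled out. Only secondary outcomes are touched, and the SAP treats their tests as more exploratory. The DXA fat-free-mass primary outcome and DXA total fat mass do not depend on this CT level.

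**What to change.** State in the abdominal CT section and in the CT work instruction that the vertebral level (disc or endplate) of the PRE slice is recorded on the localiser image. State also that POST is acquired and analysed at that same level, wherever the umbilicus then lies. Define the VAT and SAT outcomes on these level-matched slices, and report their repeatability.

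The Study Time Line runs from July 2021 to August 2023. If scanning is complete, read the PRE and POST levels from stored images where the spine can be identified, report how many differ, and run a sensitivity analysis restricted to level-matched pairs.

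The cost is a sentence of text and a little extra technician time. No additional scan should be needed, provided that the localiser shows the vertebrae; the documents do not say whether it does, so this should be confirmed first.
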